16.2 Secondary analysis

The secondary analyses will be performed for the FAS. According to previous statements, if patients have missing values for an outcome, those patients will be excluded for that outcome's analysis.

16.2.1 ICS use in the two years prior to the study visit

The secondary analyses is the proportion of patients with COPD treated with ICS at the time of study visit with or without moderate-to-severe exacerbations, in the previous 2 years before the study visit (see also section 16.1.1. Data Variables and Derivation on page 29).

This analysis will be presented according to the presence or not of moderate/severe exacerbations in the previous 2x365 days.

Use of ICS will be analyzed using number of patients in each category and percentages (absolute and relative frequencies) and 95% confidence intervals will be provided based on Wald's (Normal Approximation) method for each group. Percentages will be compared using Chi-Square test or Fisher's Exact test.

16.2.2 Moderate-to-severe exacerbations in COPD

This analysis consists of the number (count) of moderate-to-severe exacerbations in the previous 1 and 2 years previous to the study visit in COPD patients according to ICS use at time of study visit.

Document: \\bcnfs02\general\Hdmgener\MEDICAL AFFAIRS 28.02.2017 actualizada\8. SRO ESTUDIOS\RESPIRATORIO\1237-0070 NIS OPTI\11 - Clinical Trial Report\SAP\SAP - V 1.0\SAP OPTI version1.0 29052019.docx

Author:

Version Number: 1.0

Version Date: [29MAY2019]

Template No.: RWI_TP_BIOS0013 Revision 1

Reference: RWI_WI_BIOS0015

Effective Date: 15Jun2018

Copyright © 2018 All rights reserved. The contents of this document are confidential and proprietary to Holdings Inc. and its subsidiaries. Unauthorized use, disclosure or reproduction is strictly prohibited.

Patients with missing data related to exacerbations will be excluded from the analysis and number of missing values will be presented.

The objective is to describe the number (total count) of moderate-to-severe exacerbations in one and two years previous to the study visit according to ICS treatment at the time of study visit.

Results will be analyzed with measures of central tendency (mean and median), variability/dispersion (standard deviation and interquartile ranges) and ranges. The number of moderate-to-severe exacerbations will be analyzed using Mann-Whitney U test or Kruskal-Wallis non-parametric tests.

After that, at exploratory level, negative binomial regressions will be used for modelling discrete-count variables, not continuous and limited to non-negative values as the number of moderate-to-severe exacerbations (counts), both for first and second previous years. Covariates included in the model will be those used also in primary analysis, excluding the number of exacerbations in the previous year.

Backward selection procedures will be applied to generate the final model which consider only covariates in the selection procedure with a p-value <0.1 in the corresponding univariate analysis, using number of exacerbations as response variable. A p-value <0.05 will be used for the covariates to stay in the model in a backward elimination step. Continuous variables can be replaced by categorical variables.

16.2.3 General patient profile for COPD patients

To evaluate general patient profile for COPD patients, several variables will be described. In general, descriptive statistics will be used for describing the patient profile. All results will be analyzed with measures of central tendency (mean and median), variability/dispersion (standard deviation and interquartile ranges and ranges) for continuous variables and distributions of absolute and relative frequencies for categorical variables. This analysis will be also performed for the FAS.

Document: \\bcnfs02\general\Hdmgener\MEDICAL AFFAIRS 28.02.2017 actualizada\8. SRO ESTUDIOS\RESPIRATORIO\1237-0070 NIS OPTI\11 - Clinical Trial Report\SAP\SAP - V 1.0\SAP OPTI version1.0 29052019.docx

Author:

Version Number: 1.0

Version Date: [29MAY2019]

Template No.: RWI_TP_BIOS0013 Revision 1

Reference: RWI_WI_BIOS0015

Effective Date: 15Jun2018

Copyright © 2018 All rights reserved. The contents of this document are confidential and proprietary to Holdings Inc. and its subsidiaries. Unauthorized use, disclosure or reproduction is strictly prohibited.

All results will be described according to the ICS treatment in the study visit: categorical variables will be analyzed using Chi-Square or Fisher’s Exact test and quantitative variables by means t-test for independent groups or for quantitative variables that do not meet parametric applicability criteria, adequate statistical analysis will be used, as Mann-Whitney U test or Kruskal Wallis test. Variables included are:

Table 2. Variables included in the eCRF

Group	Variable
Sociodemographic	Age (years),
	gender,
	ethnicity.
	BMI (Kg/m2)
	BMI grade
	Smoking history.
Clinical Variables	Spirometry - Bronchodilator test
	Spirometry - FEV1 absolute values pre and post-bronchodilator
	Spirometry - FEV1 % values pre and post-bronchodilator.
	Spirometry - FEV1 increase from pre to post-bronchodilator
	Blood Eosinophilia (number of eosinophils and %)
	Immunoglobulin E (Ig E)
Exacerbations	Episodes of exacerbations in the previous year
	Episodes of exacerbations in the two previous years
	Episodes of severe exacerbations in the previous year
	Episodes of severe exacerbations in the two previous years
	Treatments for exacerbations
COPD characteristics	Time since COPD diagnosis (years)
	COPD GesEPOC 2017 phenotypes
	GOLD 2019 spirometric classifications (Gold 1, Gold 2, Gold 3, Gold 4).
	GOLD 2019 patient groups (A, B, C, D).
	BODEx index (numerical and categories)
	Risk classification according GesEPOC.
	Breathlessness based on mMRC score.
	CAT - COPD Assessment Test (numerical and categories)
Comorbidities	COTE index (numerical and categories)
	History of asthma (yes/no)
	Time since asthma diagnosis (years)

Document: \\bcnfs02\general\Hdmgener\MEDICAL AFFAIRS 28.02.2017 actualizada\8. SRO ESTUDIOS\RESPIRATORIO\1237-0070 NIS OPTI\11 - Clinical Trial Report\SAP\SAP - V 1.0\SAP OPTI version1.0 29052019.docx

Author: Version Number: 1.0
Version Date: [29MAY2019]

Template No.: RWI_TP_BIOS0013 Revision 1 Reference: RWI_WI_BIOS0015

Effective Date: 15Jun2018

Group	Variable
	History of atopy (yes/no).
Treatments	Current COPD treatment: With ICS: ICS, LABA+ICS, LABA+LAMA+ICS. Without ICS: SABA, SAMA, LABA, LAMA, LABA+LAMA, Others
	History of antibiotics for COPD
	History of corticosteroids for COPD
	Concomitant medication.
	Adherence to GesEPOC 2017 treatment recommendations guidelines

16.2.4 Rescue medication use

The description of Rescue medication used in patients treated with ICS and without ICS will include the active substance (ATC codes), dose, start date and end date. The main treatment is salbutamol (SABA) and it will be described the number and percentage of patients who used each treatment as rescue medication in the last year and in the last two years. This percentage will be calculated using as denominator FAS set.

Results will be stratified by ICS treatment in the study visit. Percentages will be compared using Chi-Square or Fisher’s Exact test.

16.2.5 Adherence to GesEPOC 2017 treatment recommendations guidelines

Adherence to treatment recommendations according GesEPOC 2017 guidelines will be described using number and percentage of adherent patients (considered treated according to guidelines).

Tables will be described according to the number of exacerbations in the last year prior to study visit:

- patients with 0-1 exacerbations (not leading to hospital admission) vs.
- patients with ≥ 2 exacerbations or ≥ 1 exacerbation leading to hospital admission in the last 1 year;

Comparisons between groups will be performed using Chi-Square or Fisher’s Exact test.

Document: \\bcnfs02\general\Hdmgener\MEDICAL AFFAIRS 28.02.2017 actualizada\8. SRO ESTUDIOS\RESPIRATORIO\1237-0070 NIS OPTI\11 - Clinical Trial Report\SAP\SAP - V 1.0\SAP OPTI version1.0 29052019.docx

Author: Version Number: 1.0
Version Date: [29MAY2019]

Template No.: RWI_TP_BIOS0013 Revision 1 Reference: RWI_WI_BIOS0015

Effective Date: 15Jun2018

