7.2.11 Risk stratification

Patients will be classified according to their risk based on GesEPOC 2017 Spanish guideline:

- Low risk:
 - FEV₁(%) post-bronchodilation ≥ 50% and,
 - mMRC 0-2, and
 - 0 or 1 exacerbation in the last year, and
 - without hospitalization in the last year.
- High risk:
 - FEV₁(%) post-bronchodilation <50% or,
 - mMRC > 2 or mMRC = 2 with treatment or,
 - 2 or more exacerbation in the last year or,
 - 1 or more exacerbation with hospitalization in the last year.

Document: \\bcnfs02\general\Hdmgener\MEDICAL AFFAIRS 28.02.2017 actualizada\8. SRO ESTUDIOS\RESPIRATORIO\1237-0070 NIS OPTI\11 - Clinical Trial Report\SAP\SAP - V 1.0\SAP OPTI version1.0 29052019.docx

Author: Version Number: 1.0

Version Date: [29MAY2019]

Template No.: RWI_TP_BIOS0013 Revision 1

Reference: RWI_WI_BIOS0015

Effective Date: 15Jun2018

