Table 38. Adherence to treatment recommendations according to GesEPOC 2017 Guidelines, according to number of exacerbations in the last year

		0-1 * exacerbations	>= 2 ** exacerbations	Total
Adherence	Adherent (Adequate ICS use) ICS-Treated who should be treated with ICS Non ICS-treated who should not be treated with ICS Non-Adherent (Non-adequate ICS use) ICS-Treated who should not be treated with ICS Non ICS-treated who should be treated with ICS			

* 0-1 exacerbations (not leading to hospital admission). ** ≥ 2 exacerbations or ≥ 1 exacerbation leading to hospital admission in the last 1 year prior to index date.

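### GesEPOC adherence is compared between exacerbation strata as one pooled percentage, so the comparison can show a gap when prescribing is identical

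*SAP*

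**What the plan says.** SAP 16.2.5 states that adherence "will be described using number and percentage of adherent patients (considered treated according to guidelines"). The table is split by exacerbations in the last year. One column is "patients with 0-1 exacerbations (not leading to hospital admission) vs". The other holds patients with two or more exacerbations, or at least one leading to admission. The section closes with "Comparisons between groups will be performed using Chi-Square" or Fisher's exact test. It does not name the rows to be tested.

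SAP 7.2.14 counts a patient as adherent in two ways: treated with ICS when the guideline calls for it, or not treated when it does not. It treats ICS as indicated only in high-risk patients with an exacerbator or mixed phenotype. For the two exacerbator phenotypes it also requires earlier LAMA/LABA treatment and worsening.

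SAP 7.2.11 lists among the routes to high risk "2 or more exacerbation in the last year or" at least one exacerbation with hospitalisation. Those two routes are the upper column of 16.2.5. The other routes are FEV1 and mMRC.

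SAP 16.2.3 says that all profile results are described by ICS treatment at the visit, with chi-square or Fisher's test for categorical variables. The list that follows (Table 2) includes "Adherence to GesEPOC 2017 treatment recommendations guidelines".

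**The concern.** The variable that splits the table is also an input to the rule that decides who should have ICS. The upper column is high risk in full, and the lower column is high risk only through FEV1 or mMRC. The two columns will therefore usually differ in the share of patients for whom ICS is indicated.

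The pooled percentage adds ICS correctly given to ICS correctly withheld. In the lower column the second component tends to dominate, and in the upper column the first. A difference between columns can then reflect the indication mix and not how doctors prescribe.

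Adherence is secondary outcome (h) of the protocol, and ICS overuse is the study's rationale. A p-value on the pooled figure could be read as doctors following the guideline better, or worse, in one stratum.

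The Table 2 comparison has a related problem. Among ICS users, adherent means indicated. Among non-users, adherent means not indicated. Testing one against the other compares two different quantities.

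**Working it through.** **The plan's own figures.** 0.66 × 0.61 = 0.403, the plan's 40%. 0.40 ± 1.96·√(0.40·0.60/900) = 0.40 ± 0.032, or 36.8% to 43.2%. 900/0.9 = 1,000. All reproduce.

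**Inputs**
- From the documents: 900 patients analysed, 61% ICS use (stated for non-exacerbators only), 66% non-exacerbators, two-sided 0.05.
- Assumed, because the documents do not give them: ICS use in the upper stratum, the indicated shares s0 (lower stratum) and s1 (upper stratum), and the stratum sizes.

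**Formula.** Let a = P(ICS | indicated) and b = P(ICS | not indicated), each the same in both strata, so that prescribing is identical. Pooled adherence in a stratum with indicated share s is s·a + (1−s)·(1−b). The gap between strata is (a + b − 1)(s1 − s0). If ICS use q is unrelated to indication, then a = b = q and the gap is (2q − 1)(s1 − s0).

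**Case 1: q = 0.61, s0 = 5–20%, s1 = 70–100%, upper stratum 90–180 of 900.** The multiplier is 2 × 0.61 − 1 = 0.22.
- Smallest gap (s0 = 0.20, s1 = 0.70): 0.22 × 0.50 = 11 points, 43.4% vs 54.4%. With 810/90 patients the pooled proportion is 0.445, the standard error √(0.445·0.555·(1/810 + 1/90)) = 0.0552, and z = 0.110/0.0552 = 1.99.
- Largest gap (s0 = 0.05, s1 = 1.00): 0.22 × 0.95 = 20.9 points, 40.1% vs 61.0%. With 720/180 patients the pooled proportion is 0.443, the standard error 0.0414, and z = 0.209/0.0414 = 5.05.

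**Case 2: other indicated shares and rates of ICS use.** Here the strata are 594 and 306 patients (66% and 34% of 900), with the non-exacerbator share standing in for the lower stratum.

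| q | s0 / s1 | Adherent, lower vs upper | Gap (points) | Chance of p < 0.05 |
|---|---|---|---|---|
| 0.61 | 0.1 / 0.9 | 41.2% vs 58.8% | 17.6 | 99.9% |
| 0.61 | 0.1 / 0.6 | 41.2% vs 52.2% | 11.0 | 88% |
| 0.61 | 0.2 / 0.5 | 43.4% vs 50.0% | 6.6 | 47% |
| 0.61 | 0.3 / 0.3 | 45.6% vs 45.6% | 0 | 5% |
| 0.50 | any | 50% vs 50% | 0 | 5% |
| 0.40 | 0 / 1 | 60% vs 40% | −20 | about 100% |

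For the 0.1/0.6 row, a lower stratum of 75% or 85% of patients leaves the gap at 11 points. The chance of p < 0.05 falls to 82% or 66%.

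**Case 3: prescribing that follows indication in part.** With a = 0.8 and b = 0.6 in both strata the multiplier is 0.4. Over the Case 1 ranges the gap is 0.4 × 0.50 = 20 to 0.4 × 0.95 = 38 points (z 3.6 to 9.1).

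**Comparison within indication class.** In every case above, ICS use among patients not indicated is b in both strata, and non-use among patients indicated is 1 − a in both. The expected between-strata difference is zero, as it should be.

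**Table 2 comparison.** If 20% are indicated and this is unrelated to ICS use, adherence is 20% in users and 80% in non-users. At an indicated share of 50% it would be 50% and 50%. The contrast follows the indicated share.

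**The case against.** The strongest reply has six parts.

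- **The strata do not fix the indication.** A reader might infer that they decide who should have ICS. The documents do not support that: phenotype, FEV1, mMRC and earlier LAMA/LABA also count, so a lower-stratum patient can be indicated and an upper-stratum patient need not be. This stands, and it is why the indicated shares are shown as ranges.
- **A large gap is not automatic.** A reader might infer that the test must favour exacerbators. The gap depends on ICS use and on the indicated shares, and it can be small, zero or reversed. This stands. Zero at 50% ICS use is a coincidence of inputs, though, and no safeguard.
- **Over-treatment and under-treatment are not hidden.** Table 38 gives all four treated-by-indicated cells per stratum, and protocol outcome (h) lists them separately. ICS use without exacerbations has its own analysis in SAP 16.1.3.2. This stands. What is missing is a rate with the indication class as denominator, and a statement of what is tested.
- **The test target is unspecified.** That the test falls on the pooled adherent row is an inference, but the natural one: the section's only stated summary is the "described using number and percentage of adherent patients".
- **P-values are descriptive (SAP 8.2).** This limits the consequence. It does not make the contrast of percentages interpretable as prescribing.
- **No table shell shows adherence by ICS use.** Tables 6 to 23 omit it. The Table 2 problem therefore rests on the text of 16.2.3, which includes it when read literally.

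**Conclusion.** The point holds in a limited form. The planned between-strata comparison of pooled adherence mixes the indication mix with prescribing, and it can show a difference when prescribing is the same.

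Under the Case 1 assumptions the spurious gap runs from borderline to clearly significant at the usual 5% level. With closer indicated shares it is modest, and its direction depends on whether ICS use is above or below 50%. The size rests on indicated shares and stratum sizes that the documents do not give, and on applying the 61% to all patients.

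The comparison by ICS use in Table 2 does not measure prescribing quality under any of these inputs. Each stratum's adherent percentage remains a valid description in itself.

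Importance is moderate: a secondary outcome, p-values declared descriptive, and the component cells already shown.

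**What to change.** In SAP 16.2.5 and Table 38:

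1. Add two rates per stratum, each with a 95% CI: over-treatment (ICS users among patients who should not have ICS) and under-treatment (non-users among patients who should have ICS).
2. Make any comparison between exacerbation strata within those denominators, and name the rows tested.
3. Where a denominator is small, use Fisher's exact test or description only.
4. Keep the pooled adherent percentage as description, without a test.

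In SAP 16.2.3, remove adherence from the Table 2 variables tested by ICS use.

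The cost is SAP wording and a change of denominator. No new data are needed, because both rates come from the four cells of Table 38. The price is precision in the upper stratum. With 90–180 patients and 70–100% indicated, at most 180 × 0.30 = 54 patients there should not have ICS, and possibly none, so the between-strata over-treatment comparison may not be estimable.

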16.2.6 ICS-related adverse events

Percentage of patients treated with ICS who reported ICS-related events will be reported. All adverse event list will be presented (see Safety Outcomes).

17. PATIENT REPORTED OUTCOMES (PRO)

Quality of Life (QoL) was assessed using the COPD Assessment Test (CAT), a questionnaire for people with COPD designed to measure the impact of COPD on a person's life, and how these changes over time (<http://www.catestonline.org/>).

The analysis of CAT is included in analysis of patient profile in section 16.2.3. General patient profile for COPD patients (page 33).

18. SAFETY OUTCOMES

All outputs for safety outcomes will be based on the Safety Analysis Set (see sections 6.4 and 6.5).

18.1 Adverse Drug Reactions

First of all, the percentage of patients experiencing ICS-related adverse drug reactions (ADRs) will be presented in patients using ICS. Only ADRs with onset date included in the last two years previous to study visit will be included.

Number and percentage of patients reporting each type of ADRs will be reported: Pneumonia, Fracture, Skin thinning/easy bruising, Cataract, Diabetes and Oropharyngeal candidiasis. ADRs will be described according to type, seriousness, reason for seriousness and outcome.

In the same way, the percentage of patients experiencing Adverse Drug Reactions related with BI products SPIOLTO®, STRIVERDI®, SPIRIVA® or ATROVENT® will be presented. Number and percentage of patients reporting each type of ADRs will be reported. ADRs will be described according to type, duration (days), seriousness, reason for seriousness and outcome.

Document: \\bcnfs02\general\Hdmgener\MEDICAL AFFAIRS 28.02.2017 actualizada\8. SRO ESTUDIOS\RESPIRATORIO\1237-0070 NIS OPTI\11 - Clinical Trial Report\SAP\SAP - V 1.0\SAP OPTI version1.0 29052019.docx

Author:

Version Number: 1.0

Version Date: [29MAY2019]

Template No.: RWI_TP_BIOS0013 Revision 1

Reference: RWI_WI_BIOS0015

Effective Date: 15Jun2018

Copyright © 2018 All rights reserved. The contents of this document are confidential and proprietary to Holdings Inc. and its subsidiaries. Unauthorized use, disclosure or reproduction is strictly prohibited.

Adverse Drug Reaction term (open string variable) will be coded using Medical Dictionary for Regulatory Activities (MedDRA) central coding dictionary, Version 20.0.

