9.2.3 Study visits

The design of the study impose an only one visit to be performed that will coincide with one of those performed by the patients as part of routine follow-up of their disease, without interfering with usual clinical practice of the investigator.

After signing the informed consent (if patient agreed to participate in the study) patients will be asked to answer the breathlessness scale (mMRC) and the CAT – COPD Assessment Test at the unique study visit. Other variables needed to answer study objectives will be obtained directly from patient medical records. The end of the study visit is the end of the study for each patient.

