9.3.2.2 Secondary outcomes

The secondary outcomes are:

- a) To describe the proportion of patients currently on ICS who have had moderate/severe exacerbation in the year prior to the study visit.
- b) Proportion of patients with COPD treated with ICS at the time of study visit with or without moderate-to-severe exacerbations, in the previous 2 years before the study visit.
- c) Proportion of patients with COPD not treated with ICS at the time of study visit with or without moderate-to-severe exacerbations, both in the previous 1 year and previous 2 years before the study visit.
- d) Number (count) of moderate-to-severe exacerbations in COPD patients treated with ICS at the time of study visit, both in the previous 1 year and previous 2 years before the study visit.
- e) Number (count) of moderate-to-severe exacerbations in COPD patients not treated with ICS at the time of study visit, both in the previous 1 year and previous 2 years before the study visit.
- f) General patient profile for patients treated with ICS and patients not treated with ICS. These data will be obtained from medical charts.
- g) Description of Rescue medication used in patients treated with ICS and without ICS (active substance, dose, start date, end date). These data will be obtained from medical charts.
- h) Adherence to treatment recommendations according GesEPOC 2017 guidelines. For this analysis, patients will be stratified between patients with 0-1 exacerbations (not leading to hospital admission) and for patients with ≥ 2 exacerbations or ≥ 1 exacerbation leading to hospital admission in the last 1 year prior to index date. Taking into account the algorithm of treatment recommendations included in GesEPOC (phenotype) guidelines, we will define:

- Adherence:
 - Those patients (%) treated with ICS that according to GesEPOC guidelines should have been treated with ICS.
 - Those patients (%) not treated with ICS that according to GesEPOC guidelines should not have been treated with ICS.
 - Non-Adherence:
 - Those patients (%) treated with ICS but according to GesEPOC guidelines should not have been treated with ICS.
 - Those patients (%) not treated with ICS but according to GesEPOC guidelines should have been treated with ICS.
- i) To describe ICS-related adverse events (Pneumonia, Fracture, Skin thinning/easy bruising, Cataract, Diabetes, Oropharyngeal candidiasis). These data will be obtained from medical charts.

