11.2 ADVERSE EVENT AND SERIOUS ADVERSE EVENT COLLECTION AND REPORTING

The investigator shall maintain and keep detailed records of all AEs in their patient files.

Collection of AEs

The study design is of non-interventional nature and the study is conducted within the conditions of the approved marketing authorisation. Sufficient data from controlled interventional trials are available to support the evidence on the safety and efficacy of the studied BI drug. For this reason the following AE collection and reporting requirements have been defined.

The following must be collected by the investigator in the (e)CRF from signing the informed consent onwards until the end of the study:

- All adverse drug reaction (ADRs) (serious and non-serious).
- All AEs with fatal outcome.

All ADRs , including those persisting after study completion must be followed up until they are resolved, have been sufficiently characterized, or no further information can be obtained.

The investigator carefully assesses whether an AE constitutes an ADR using the information below.

Causal relationship of adverse event

The definition of an adverse reaction implies at least a reasonable possibility of a causal relationship between a suspected medicinal product and an adverse event. An adverse reaction, in contrast to an adverse event, is characterised by the fact that a causal relationship between a medicinal product and an occurrence is suspected.

Medical judgment should be used to determine the relationship, considering all relevant factors, including pattern of reaction, temporal relationship, de-challenge or re-challenge, confounding factors such as concomitant medication, concomitant diseases and relevant history.

Arguments that may suggest **a reasonable causal relationship** could be:

- The event is **consistent with the known pharmacology** of the drug
- The event is known to be caused by or **attributed to the drug class**.
- A **plausible time to onset of the event** relative to the time of drug exposure.
- Evidence that the **event is reproducible** when the drug is re-introduced

- **No medically sound alternative etiologies** that could explain the event (e.g. preexisting or concomitant diseases, or co-medications).
- The event is typically **drug-related and infrequent in the general population** not exposed to drugs (e.g. Stevens-Johnson syndrome).

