		Current Non - ICS	Current ICS	Total ICS patients
ADRs associated to BI product	Total Patients No Yes			
Type of ADR (multi-response)	Term 1 Term 2 ... Term n			
ADR outcome (multi-response)	Recovered Not yet recovered Recovered with secuelae Unknown Fatal			

Patients in the Safety Analysis Set. Including patients treated with BI product at some time during the previous two years.

Table 45. Description of ADRs associated to BI product according to current treatment on ICS

		Current Non - ICS	Current ICS	Total ICS patients
--	--	-------------------	-------------	--------------------

Document: \\bcnfs02\general\Hdmgener\MEDICAL AFFAIRS 28.02.2017 actualizada\8. SRO ESTUDIOS\RESPIRATORIO\1237-0070 NIS OPTI\11 - Clinical Trial Report\SAP\SAP - V 1.0\SAP OPTI version1.0 29052019.docx

Author: Version Number: 1.0
Version Date: [29MAY2019]

Template No.: RWI_TP_BIOS0013 Revision 1 Reference: RWI_WI_BIOS0015

Effective Date: 15Jun2018

		Current Non - ICS	Current ICS	Total ICS patients
ADRs associated to BI product	Total ADRs			
Type of ADR	Term 1 Term 2 ... Term n			
ADR outcome	Recovered Not yet recovered Recovered with secuelae Unknown Fatal			

Patients in the Safety Analysis Set. Including patients treated with BI product at some time during the previous two years

Table 46. List of ADRs associated with BI product.

PATCOD	Adverse Event Term	MedDRA Code	Onset date	End date	SAE?	Reason for seriousness	Outcome	Relationship With BI product	BI product

Patients in the Safety Analysis Set. Including patients treated with BI product at some time during the previous two years

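### SAP 18.1-18.2 and Tables 44-48 report BI-product reactions as percentages of two-year users, although protocol 11.2 requires their collection only from consent to the end of the single visit

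*SAP*

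**What the plan says.** **Collection.** Protocol 11.2 states that all adverse drug reactions, and all adverse events with a fatal outcome, "must be collected by the investigator in the (e)CRF from signing the informed consent onwards until the end of the study". The expedited-reporting table in the same section, which names SPIOLTO, STRIVERDI, SPIRIVA and ATROVENT, has the same start and end. Protocol 9.2.3 fixes the end: "The end of the study visit is the end of the study for each patient".

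**Separate source for ICS events.** Protocol 9.3.2.2, item i, reads: "To describe ICS-related adverse events (Pneumonia, Fracture, Skin thinning/easy bruising, Cataract, Diabetes, Oropharyngeal candidiasis). These data will be obtained from medical charts". There is no matching provision for BI-product reactions.

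**Analysis.** In its ICS paragraph SAP 18.1 says "Only ADRs with onset date included in the last two years previous to study visit will be included". A later paragraph begins "In the same way, the percentage of patients experiencing Adverse Drug Reactions related with BI products" and gives no onset window of its own. It adds: "ADRs will be described according to type, duration (days), seriousness, reason for seriousness and outcome". SAP 18.2 repeats the two-year restriction for serious ICS reactions. Its BI-product paragraph has neither that restriction nor a linking phrase.

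**Denominator.** SAP 6.5 takes enrolled patients with at least one dose of a BI product in the study period, and SAP 14 uses that term for the two years before the visit. The footnote to Tables 44-48 says "Including patients treated with BI product at some time during the previous two years".

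**Changes from protocol.** SAP 4.6 declares none.

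**The concern.** A percentage of patients with a reaction is interpretable only if numerator and denominator refer to the same observation period. Here the denominator reaches back two years, while the required recording of BI-product reactions begins at consent and ends with the visit. If the two-year onset filter also applies to these reactions, it selects onset before the visit from records that need only hold events from consent onwards. A reaction that starts at the visit could then fail the filter, while one that passes it need not have been recorded.

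What is at stake is a small or zero percentage in the study report, set beside ICS tables that do cover two years. It would look like a low two-year reaction risk for the sponsor's products, when that period was not systematically observed.

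**Working it through.** **Inputs from the documents**
- Required window for BI-product reactions: consent to end of visit (protocol 11.2 and 9.2.3), taken as at most 1 day.
- Two years: 730.5 days (SAP 7.2.6.1, defined there for exacerbations).
- Expected BI-product reaction rate and number of BI-product users: not given. Assumed here: two-year risk R from 1% to 30%, and N from 100 to 1,000 users.

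**The plan's own figure.** The documents give no figure for reactions. The only planned precision is for the ICS proportion: 0.40 ± 1.96 × √(0.40 × 0.60 / 900) = 0.40 ± 0.032, that is 36.8% to 43.2%, and 900 / 0.9 = 1,000. Both reproduce, and neither is affected by this point.

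**Share of the period observed.** 1 / 730.5 = 0.137%.

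**Expected counts.** With a constant hazard, the one-day risk is q = 1 − (1 − R)^(1/730.5). The expected number of patients with a reaction is N × q, and the chance that none is recorded is (1 − q)^N. For N = 500:

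| Assumed two-year risk R | Patients if two years were collected (N × R) | One-day risk q | Expected patients, one-day window | Chance of an empty table |
|---|---|---|---|---|
| 1% | 5 | 0.0014% | 0.007 | 0.993 |
| 5% | 25 | 0.0070% | 0.035 | 0.966 |
| 10% | 50 | 0.0144% | 0.072 | 0.930 |
| 20% | 100 | 0.0305% | 0.153 | 0.858 |
| 30% | 150 | 0.0488% | 0.244 | 0.783 |

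Over the same range of R, the chance of an empty table is 95% to 99.9% for N = 100 and 61% to 99% for N = 1,000.

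**What a zero would mean.** The exact two-sided 95% upper limit for 0 of n is 1 − 0.025^(1/n): 2.4% for n = 150, 1.2% for n = 300 and 0.8% for n = 450 (all assumed numbers of users). The shells of Tables 44 and 47 have no row for an interval, so the report would not print this limit. A reader who worked it out would be bounding about one day of observation, not two years.

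**ICS tables.** The six named events come from charts (protocol 9.3.2.2, item i), so a two-year onset filter fits their source. The mismatch is confined to Tables 44-48. The columns of those tables are still headed as totals of ICS patients, which suggests that the ICS shells were reused without their data source.

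**The case against.** Several points count against a stronger statement.

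- A reader might infer that the protocol collects all drug reactions only from consent. It does not, because the six ICS events are retrospective.
- A reader might infer that the SAP expressly filters BI-product reactions on a two-year onset. It does not. The restriction stands in the ICS paragraph of 18.1 and reaches BI products only through a linking phrase, which could refer merely to presenting a percentage. In 18.2 even that link is absent. The footnotes define who was exposed, not when a reaction began.
- A reader might infer that the tables are bound to show near zero. Protocol 11.2 can be read as the period in which reactions must be recorded, not as a limit on onset date. The CRF behind the SAP (version 1.0) is not among the documents, and it may ask for earlier reactions. The planned duration in days, and the onset and end dates in Table 46, could point that way. They are not decisive, since protocol 11.2 also requires reactions that persist after the study to be followed up.
- BI-product reactions are not a study objective or outcome, and the study is not a PASS. Protocol 11.2 itself says that sufficient safety and efficacy data come from controlled trials.

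These points limit the claim but do not remove it. Even if the CRF allows earlier reactions to be entered, the protocol does not require investigators to look for them, so what is recorded would be incomplete by an unknown amount. The two-year denominator stays mismatched whether or not the onset filter applies. Taking the end of study to be the last patient's visit does not help either, because Annex 2 states that no follow-up is carried out.

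**Conclusion.** The point holds for BI-product reactions and serious reactions in SAP 18.1-18.2 and Tables 44-48, and only there. Under protocol 11.2 as written, reactions before consent are not systematically ascertained. A percentage over patients exposed in the previous two years therefore cannot be read as a two-year risk, and would probably be close to zero.

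The calculated size rests on a one-day window, a constant hazard, and assumed risks and numbers of users. The direction needs only the mismatch between the two periods. The word probably is deliberate: the content of the CRF is unknown, and the documents do not show that the tables must be empty. The primary outcome, the secondary outcomes and the study size are unaffected. The change is still worth making, because the number as planned is uninterpretable safety information about the sponsor's own products.

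**What to change.** 1. In SAP 18.1, 18.2 and Tables 44-48, state that BI-product reactions are those recorded under protocol 11.2, from consent to the end of the visit, and that the two-year onset filter does not apply to them.
2. Present counts and the listing, without percentages over patients exposed in the previous two years. Tables 45 and 48 already count events and Table 46 is already a listing, so the main change is to the percentages in the text and in Tables 44 and 47.
3. List separately any BI-product reactions with earlier onset that were recorded, with a note that they were not systematically collected. Do not drop them.
4. Name chart abstraction (protocol 9.3.2.2, item i) as the source of the two-year ICS tables.
5. Record the clarification in SAP 4.6.

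The cost is SAP wording, table titles and footnotes, with no new data. The downside is that there will be no two-year percentages for BI products, which the required data collection does not support.
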